5.3.2 Cobimetinib Dosage, Storage, and Administration

The recommended dose for cobimetinib is 60 mg OD for 21 days on, then 7 days off, in a 28 day treatment cycle. The 20 mg cobimetinib drug product is a film-coated, immediate release tablet. The white tablet is round with the engraving "ROCHE" on one side. Tablet imprint is "COB". Cobimetinib will be packaged in blister packs. Cobimetinib should not be stored above 25°C (77°F).

Cobimetinib should be taken once daily at approximately the same time each day and no later than 4 hours after the scheduled time. Cobimetinib can be taken with or without a meal. Cobimetinib tablets should never be chewed, cut, or crushed. At least 7 days off cobimetinib is required prior to starting a new treatment cycle.

Cobimetinib will be supplied by Genentech Inc. as tablets. The 20-mg cobimetinib drug product is a film-coated, white, round, immediate-release tablet. Cobimetinib will be packaged in blister packs. The inactive ingredients in cobimetinib are as follows: lactose monohydrate, microcrystalline cellulose, croscarmellose sodium, and magnesium stearate for the tablet core. The tablet coating consists of polyvinyl alcohol part hydrolyzed, titanium dioxide, polyethylene glycol 3350, and talc. Cobimetinib should not be stored above 25°C (77°F). If the study drug is

stored outside of the permitted temperature ranges, quarantine the affected supply and contact the monitor.

Guidelines for treatment interruption or discontinuation and the management of specific adverse events are provided in Section 5.5 and Appendix 7. For further details, see the cobimetinib Investigator's Brochure.

Cobimetinib may be prepared, handled, and administered per the current FDA-approved package insert.

Cobimetinib compliance will be monitored by study team. Prior to start of each new cycle, patient compliance will be evaluated and documented in eCRF by asking patients about amount of drug consumed and pill counts. Study team will question patients regarding any discrepancies and document the explanation. The returned drug by patient will be documented by study team in eCRF.

5.3.3 Investigational Medicinal Product Accountability

All IMPs required for completion of this study (atezolizumab and cobimetinib) will be provided by the Genentech Inc. where required by local health authority regulations. The study site will acknowledge receipt of IMPs by returning the appropriate documentation form to confirm the shipment condition and content. Any damaged shipments will be replaced.

Any unused drug will be destroyed according to MDACC's standard operating procedure or will be returned to the Genentech Inc. with the appropriate documentation. The site's method of IMP destruction must be agreed to by the Genentech Inc. The site must obtain written authorization from the Genentech Inc. before any IMP is destroyed, and IMP destruction must be documented on the appropriate form.

Accurate records of all IMPs received at, dispensed from, returned to, and disposed of by the study site should be recorded on the Drug Inventory Log.

5.3.4 Dosing of Study Treatment Beyond Disease Progression

Dosing of study treatment beyond RECIST v1.1-defined disease progression is allowed for patients on all treatment arms. Patients must meet all of the following criteria to be allowed to receive study treatment beyond disease progression:

- Evidence of clinical benefit as assessed by the investigator
- Absence of symptoms and signs indicating unequivocal progression of disease. Patients may continue to receive treatment beyond disease progression in the absence of clinical signs or symptoms of progression despite a rising CEA level.
- No decline in ECOG performance status that can be attributed to disease progression.
- Absence of tumor progression at critical anatomical sites (e.g., leptomeningeal disease) that cannot be managed by protocol-allowed medical interventions.
- Patients must provide written consent to acknowledge deferring these treatment options in favor of continuing study treatment at the time of RECIST v1.1-defined disease progression.
- Approved by the Investigator
- Patients will need to sign a separate treatment beyond progression consent

5.4 CONCOMITANT THERAPY, PROHIBITED FOOD, AND ADDITIONAL RESTRICTIONS

Concomitant therapy includes any medication (e.g., prescription drugs, over-the-counter drugs, vaccines, herbal or homeopathic remedies, nutritional supplements) used by a patient from 7 days prior to initiation of study drug to treatment discontinuation visit. All such medications should be reported to the investigator and recorded in the eCRF.

5.4.1 Permitted Therapy

The following therapies are permitted in the study:

- Hormonal therapy with gonadotropin-releasing hormone agonists or antagonists for prostate cancer
- Oral contraceptives
- Hormone-replacement therapy
- Prophylactic or therapeutic anticoagulation therapy (such as low-molecular weight heparin or warfarin at a stable dose level)
- Palliative radiotherapy (e.g., treatment of known bone metastases) provided it does not interfere with assessment of tumor target lesions. It is not required to withhold avelozumab during palliative radiotherapy.
- Surgery (preferable) or definitive radiation therapy (with or without radiosensitizing agent) for patients specifically enrolled in the cutaneous squamous cell carcinoma cohort when upfront surgery was considered functionally or cosmetically inappropriate is allowed after a minimum of two cycles of therapy with the investigational agents.
- Inactive influenza vaccinations during influenza season ONLY
- Megestrol administered as an appetite stimulant
- Inhaled corticosteroids for chronic obstructive pulmonary disease
- Mineralocorticoids (e.g., fludrocortisone)

Anti-emetics and anti-diarrheal medications should not be administered prophylactically before initial treatment with study drugs. At the discretion of the investigator, prophylactic anti-emetic and anti-diarrheal medication(s) may be used per standard clinical practice before subsequent doses of study drugs. Hematopoietic growth factors should not be administered prophylactically before initial treatment with study drugs. Hematopoietic growth factors may be administered according to local guidelines if indicated during the course of the study.

In general, investigators should manage a patient's care with supportive therapies as clinically indicated, as per local standards. Patients who experience infusion-associated symptoms may be treated symptomatically with acetaminophen, ibuprofen, diphenhydramine, and/or famotidine or another H2 receptor antagonist as per standard practice (for sites outside the United States, equivalent medications may be substituted per local practice). Serious infusion-associated events manifested by dyspnea, hypotension, wheezing, bronchospasm, tachycardia, reduced oxygen saturation, or respiratory distress should be managed with supportive therapies as clinically indicated (e.g., supplemental oxygen and b2-adrenergic agonists).

All medications must be recorded on the Concomitant Medications eCRF.

5.4.2 Therapy Not Permitted

Any concomitant therapy intended for the treatment of cancer, whether health authority-approved or experimental, is prohibited for various time periods prior to starting study treatment, depending on the anti-cancer agent, and during study treatment until disease progression is documented and patient has discontinued study treatment. This includes but is not limited to chemotherapy, hormonal therapy, immunotherapy, radiotherapy, investigational agents, or herbal therapy.

The following medications are prohibited while receiving study treatment, unless otherwise noted:

- Traditional herbal medicines as their use may result in unanticipated drug-drug interactions that may cause or confound assessment of toxicity.
- Any live, attenuated vaccine (e.g., FluMist®) within 4 weeks prior to treatment start date or at any time during the study or within 90 days following the last infusion of atezolizumab.
- For patients on atezolizumab:
 - Use of steroids to premedicate patients for whom CT scans with contrast are contraindicated (i.e., patients with contrast allergy or impaired renal clearance); in such patients, MRIs of the chest, abdomen, and pelvis with a non-contrast CT scan of the chest must be performed.
 - Immunomodulatory agents, including but not limited to interferons or IL-2, during the entire study; these agents could potentially increase the risk for autoimmune conditions when received in combination with atezolizumab
 - Immunosuppressive medications, including but not limited to cyclophosphamide, azathioprine, methotrexate, and thalidomide; these agents could potentially alter the activity and the safety of atezolizumab
 - Systemic corticosteroids and TNF- α inhibitors may attenuate potential beneficial immunologic effects of treatment with atezolizumab. Therefore, in situations where systemic corticosteroids or TNF- α inhibitors would be routinely administered, alternatives, including antihistamines, should be considered first by the treating physician. If the alternatives are not feasible, systemic corticosteroids and TNF- α inhibitors may be administered at the discretion of the treating (see Section 4.4.2)
- For patients on cobimetinib:
 - Concomitant use of strong and moderate inhibitors of CYP3A (e.g., clarithromycin, grapefruit juice, itraconazole, ketoconazole, posaconazole, telithromycin, and voriconazole) should be avoided as cobimetinib is a sensitive substrate of CYP3A and exposures will be increased in presence of these agents (approximately 7-fold increase in presence of itraconazole in healthy subjects).
 - Avoid strong and moderate CYP3A inducers (e.g., rifampin, phenytoin, carbamazepine, phenobarbital, and St. John's wort) as they increase the metabolism of cobimetinib. Strong inducers of CYP3A4 should be avoided, or selection of an alternate concomitant medicinal product, with no or minimal potential to induce CYP3A4 should be considered.

Patients will be given a list of these prohibited medications at the time of consent.

The above lists of medications are not necessarily comprehensive. Thus, the investigator should consult the prescribing information for any concomitant medication as well as the Internet references provided below when determining whether a certain medication is metabolized by or strongly inhibits or induces CYP3A or UGT2B7.

<http://www.fda.gov/downloads/Drugs/GuidanceComplianceRegulatoryInformation/Guidances/UCM292362.pdf>

<http://medicine.iupui.edu/clinpharm/ddis/table.aspx>

5.5 STUDY TREATMENT MODIFICATIONS

Guidelines for dose modifications, interruptions, or discontinuations of atezolizumab and/or cobimetinib provided below are not intended to replace the investigator's best clinical judgment with regard to the medical management of her/his individual patients.

5.5.1 Dose Modifications for Cobimetinib

NOTE: Investigators can interrupt dosing of atezolizumab (or cobimetinib) depending on the attribution of the toxicity, which is at the discretion of the investigator. During this time, treatment may continue with the other non-attributable treatment agent.

NOTE: If either atezolizumab or cobimetinib are discontinued, dosing with the other drug may continue at the discretion of the investigator.

NOTE: For Grade ≥ 3 toxicities associated primarily with laboratory abnormalities only, study treatment may continue without interruption and/or dose reduction at the discretion of the investigator per institutional practice.

Table 2: Recommended Cobimetinib Dose Modifications

Grade (CTCAE)	Recommended dose modification
Grade 1 or Grade 2 (tolerable)	No dose reduction. Maintain cobimetinib at the same dose of 60 mg QD (3 tablets)
Grade 2 (intolerable) or Grade 3 or 4 (any)*	
First appearance	Interrupt treatment until Grade ≤ 1 , restart treatment at 40 mg QD (2 tablets)
Second appearance	Interrupt treatment until Grade ≤ 1 , restart treatment at 20 mg QD (1 tablet)
Third appearance	Consider permanent discontinuation

* If cobimetinib is withheld for > 28 days because of toxicity, the patient should be discontinued from cobimetinib, unless resumption of treatment is approved by the Medical Monitor after discussion with the investigator.

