5.3 STUDY TREATMENT

This is a phase IIA, open-label study of cobimetinib and atezolizumab. All patients enrolled on study will receive cobimetinib 60 mg orally on Days 1–21 plus atezolizumab 840 mg IV on Day 1 and Day 15 in a 28-day cycle. For patient who have discontinued cobimetinib, atezolizumab can be given IV at 1680 mg once every 4 weeks.

The Investigator of the study will ensure maintenance of complete and accurate records of the receipt, dispensation, and disposal or return of all atezolizumab and cobimetinib in accordance with 21 Code of Federal Regulations (CFR), Part 312.57 and 312.62 and Genentech requirements.

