5.5.2 Dose Modifications for Atezolizumab

There will be no dose modifications for atezolizumab.

Table 3: Recommended guidelines for management of general adverse events Atezolizumab Dose Modifications.

Grade (CTCAE)	Recommended dose modification
Grade 1 or 2	No action required

Grade 3 and 4	
• Interrupt dosing of atezolizumab.• If AE resolves to Grade \leq 1, then restart dosing of atezolizumab at fixed dose level.• If the AE does not resolve to Grade \leq 1 permanently discontinue atezolizumab.• If the Grade 3/4 AE recurs (a second time), atezolizumab should be discontinued.
---------------	--

Additional guidelines for specific adverse events are provided in the subsections below and the specific management guidelines are highlighted in Appendix 7 for cobimetinib plus atezolizumab.

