AST/ALT > $3 \times$ baseline values to $< 5 \times$ ULN with total bilirubin $< 2 \times$ ULN (Grade 2)	
 Continue all study treatment. Monitor LFTs at least weekly. Consider referral to a hepatologist and liver biopsy. For suspected immune related events of > 5 days duration 
 Consider withholding atezolizumab^c Consider administering 1-2 mg/kg/day oral prednisone or equivalent followed by ≥ 1 month taper Restart atezolizumab if event resolves to Grade 1 or better within 12 weeks^{a, b} Permanently discontinue atezolizumab and cobimetinib if event does not resolve to Grade 1 or better within 12 weeks^{a, b, c}
AST/ALT > $5 \times$ baseline values to $< 10 \times$ ULN with total bilirubin $< 2 \times$ ULN (Grade 3)	
 Continue all study treatment. Monitor LFTs at least weekly. Consider referral to a hepatologist and liver biopsy. For suspected immune related events 
 Withhold atezolizumab Consider administering 1-2 mg/kg/day oral prednisone or equivalent followed by ≥ 1 month taper If event does not improve within 48 hours after initiating corticosteroids, consider adding an immunosuppressive agent. If event resolves to Grade 1 or better, taper corticosteroids over ≥ 1 month. Permanently discontinue atezolizumab and cobimetinib if event does not resolve to Grade 1 or better within 12 weeks^{a, b, c}
AST/ALT > $3 \times$ ULN with bilirubin $> 2 \times$ ULN	
 Withhold atezolizumab and cobimetinib. Consult hepatologist and consider liver biopsy. Consider administering 1-2 mg/kg/day oral prednisone or equivalent followed by ≥ 1 month taper (for possible autoimmune hepatitis). If LFTs do not decrease within 48 hr after initiation of systemic steroids, consider adding an immunosuppressive agent (e.g., mycophenolate or TNF-α antagonist). Monitor LFTs every 48–72 hr until decreasing and then follow weekly. Restart atezolizumab at fixed dose and cobimetinib at 1 dose reduction after discussion with medical monitor if AST/ALT $< 3 \times$ ULN with bilirubin $< 2 \times$ ULN and steroid dose < 10 mg oral prednisone equivalent per day.^{a, b, c} Permanently discontinue atezolizumab and cobimetinib for life-threatening hepatic events, and contact the Medical Monitor.

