AST/ALT > 10 × ULN	
• Permanently discontinue atezolizumab and cobimetinib.^c• Consult hepatologist and consider liver biopsy.• Consider administering 1–2 mg/kg/day oral prednisone or equivalent (for possible autoimmune hepatitis). If event resolves to Grade 1 or better, taper corticosteroids over \geq 1 month.• If LFTs do not decrease within 48 hr after initiation of systemic steroids, addition of an alternative immunosuppressive agent (e.g., mycophenolate or TNF-α antagonist) or dose escalation of corticosteroids may be considered.• Monitor LFTs every 48–72 hr until decreasing and then follow weekly.
--------------------	--

ULN = upper limit of normal.

^a If corticosteroids have been initiated, they must be tapered over \geq 1 month to \leq 10 mg/day oral prednisone or equivalent before atezolizumab can be resumed.

^b Atezolizumab may be withheld for a period of time beyond 12 weeks to allow for corticosteroids to be reduced to \leq 10 mg/day oral prednisone or equivalent.

The acceptable length of the extended period of time must be agreed upon by the investigator and the Medical Monitor.

^c Resumption of atezolizumab may be considered in patients who are deriving benefit and have fully recovered from the immune-related event. Patients can be rechallenged with atezolizumab only after approval has been documented by both the investigator (or an appropriate delegate) and the Medical Monitor.

DERMATOLOGIC TOXICITY

Treatment-emergent rash has been associated with atezolizumab and cobimetinib. The majority of the cases of rash were mild in severity and self-limited, with or without pruritus.

A dermatologist should evaluate persistent and/or severe rash or pruritus. A biopsy should be considered unless contraindicated.

Dermatologic toxicity and rash should be managed according to the guidelines in [**Table A3-3.**](#)

Table A3-3 Guidelines for Managing Atezolizumab and Cobimetinib Rash

Event	Action to Be Taken
Dermatologic toxicity	

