Asymptomatic CPK elevation, Grade 4	
 Withhold cobimetinib and atezolizumab treatment. If improved to Grade \leq 3 within 4 weeks, restart cobimetinib at a dose reduced by 20 mg, if clinically indicated. If not, permanently discontinue cobimetinib. Resumption of atezolizumab may be considered in patients who are deriving benefit.
Rhabdomyolysis or symptomatic CPK elevations	
 Withhold cobimetinib and atezolizumab treatment. If event improves by at least one grade and symptoms resolve within 4 weeks, restart cobimetinib at a dose reduced by 20 mg, if clinically indicated. If not, permanently discontinue cobimetinib. Resumption of atezolizumab may be considered in patients who are deriving benefit after discussion with the Medical Monitor.
Hemorrhage	
Grade 3 hemorrhage other than cerebral hemorrhage	
 Withhold cobimetinib. Continue atezolizumab. Clinical judgment should be applied when considering whether cobimetinib should be resumed. There are no data on the effectiveness of cobimetinib dose modification for hemorrhage events. If cobimetinib cannot be resumed within 28 days, permanently discontinue cobimetinib.
Grade 4 hemorrhage or any grade cerebral hemorrhage	
 Permanently discontinue cobimetinib if the event is attributed to cobimetinib; otherwise, withhold cobimetinib. Continue atezolizumab. Clinical judgment should be applied when considering whether cobimetinib should be resumed. There are no data on the effectiveness of cobimetinib dose modification for hemorrhage events.

CPK = creatine phosphokinase.

Event	Action to Be Taken
Grade 3 or 4 or intolerable	
 Withhold atezolizumab and cobimetinib.
Grade 2 treatment-related toxicities not described above	
 If event resolves to Grade 1 or better within 12 weeks, resume atezolizumab at fixed dose. If not, permanently discontinue atezolizumab. ^{a,b,c} If event resolves to Grade 1 or better within 28 days, resume cobimetinib with dose reduced by one level. If not, permanently discontinue cobimetinib.

^a If corticosteroids have been initiated, they must be tapered over \geq 1 month to \leq 10 mg/day oral prednisone or equivalent before atezolizumab can be resumed.

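### The laboratory-only NOTE in Section 5.5.1 permits uninterrupted dosing for two Grade ≥3 events for which Appendix 6 withholds or stops both drugs, and nothing says which text governs

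*Combined protocol and SAP*

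**What the plan says.** Section 5.5.1 sits under the cobimetinib heading, but its third NOTE speaks of study treatment as a whole. Section 5.3, titled Study Treatment, covers both drugs: "This is a phase IIA, open-label study of cobimetinib and atezolizumab". The NOTE applies to Grade ≥3 "toxicities associated primarily with laboratory abnormalities only" and states that "study treatment may continue without interruption and/or dose reduction at the discretion of the investigator per institutional practice".

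Four other places deal with the same grades:

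- **Section 5.5.1, Table 2 (cobimetinib).** Directly below the NOTE, the row "Grade 2 (intolerable) or Grade 3 or 4 (any") calls for interruption and restart at a lower dose.
- **Section 5.5.2, Table 3 (atezolizumab).** For Grade 3 and 4 events: "Interrupt dosing of atezolizumab". There is no laboratory exception.
- **Appendix 6, event-specific rows.** AST/ALT above 10 times ULN: "Permanently discontinue atezolizumab and cobimetinib". AST/ALT above 3 times ULN with bilirubin above 2 times ULN: "Withhold atezolizumab and cobimetinib". Asymptomatic Grade 4 CPK elevation: "Withhold cobimetinib and atezolizumab treatment".
- **Appendix 6, catch-all row.** Treatment-related Grade 3 or 4 (or intolerable Grade 2) toxicities without a row of their own: both drugs are withheld, again with no laboratory exception.

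On routing, Section 6.1.2.7 and the hepatotoxicity text of Appendix 6 send liver-test abnormalities to the Appendix 6 guidance. Sections 5.5.2, 5.5.3 and 5.5.4 send the reader to Appendix 7 for event-specific management. In this version Appendix 7 is Anaphylaxis Precautions.

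**The concern.** An asymptomatic patient with ALT at, say, 12 times ULN falls under two texts. Under the NOTE the investigator may keep both drugs going unchanged. Under Appendix 6 both are permanently stopped. The same split arises for asymptomatic Grade 4 CPK.

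Three things are at stake.

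- **Patient safety.** The NOTE as written permits dosing that another rule in the same protocol halts. Section 6.4.2.10 lists AST/ALT above 10 times ULN as an adverse event of special interest for each drug.
- **Approval.** Footnote c in Appendix 6 allows atezolizumab rechallenge only after documented approval by both the investigator and the Medical Monitor. If the NOTE is followed there is no interruption, so that approval step is never reached.
- **Consistency of conduct.** Two patients with the same value could be managed in opposite ways, each in apparent compliance. A monitor could not tell whether continued dosing is a deviation to be documented under Section 9.2.

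**Working it through.** No sample size, power or event count enters this point, so the check is a comparison of texts. For each laboratory-defined event it asks whether the NOTE applies (Grade ≥3, laboratory only) and whether the other rule allows uninterrupted dosing.

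| Event | Within the NOTE? | Other rule | Result |
|---|---|---|---|
| AST/ALT >10 × ULN (Table A3-2) | Yes. Appendix 6 labels >5 × baseline to <10 × ULN as Grade 3, and this lies above that band | Permanently stop both | Conflict |
| Asymptomatic CPK, Grade 4 (Table A3-7) | Yes. Grade ≥3, and free of symptoms by the row's own title | Withhold both; any cobimetinib restart, if clinically indicated, is 20 mg lower | Conflict |
| AST/ALT >3 × ULN with bilirubin >2 × ULN (Table A3-2) | In part. The row has no grade label, and its lower enzyme range overlaps the range labelled Grade 2 when bilirubin is <2 × ULN | Withhold both | Conflict only where Grade ≥3 |
| Laboratory-only, treatment-related Grade 3 or 4 event without its own row (catch-all) | Yes | Withhold both | Conflict |
| Laboratory-only Grade 3 or 4 event, atezolizumab (Table 3) | Yes | Interrupt atezolizumab | Conflict |
| Grade 3 AST/ALT <10 × ULN, bilirubin <2 × ULN, no suspected immune cause (Table A3-2) | Yes | Continue both | Agreement |
| Asymptomatic CPK, Grade 3 (Table A3-7) | Yes | Continue both | Agreement |

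Two further steps:

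1. **Could the NOTE be meant only as an exception to Table 2?** Its position directly above that table suggests so. Its wording does not: it is not limited to cobimetinib or to the table.
2. **Does any text rank the rules?** Section 5.5 preserves investigator judgment in general terms. Section 5.5.2 calls the event-specific rules additional. Section 6.1.2.7 and Appendix 6 direct liver-test abnormalities to the specific guidance. None of these says what happens when the NOTE and Appendix 6 differ. For CPK the routing is weaker still, because Section 6.1.2.5 also cites Appendix 7.

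**The case against.** The best defence is that the protocol runs from general to specific. The NOTE is a general permission placed above a general table, and Appendix 6 then supplies event-level guidance to which liver abnormalities are expressly directed. An experienced investigator would probably apply the specific row. The NOTE is also only permissive, Table 2 and Table A3-7 are titled as recommendations, Appendix 6 is headed as guidelines, and Section 5.5 says its own guidance does not displace clinical judgment.

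Much of this stands. It would be too strong to say that Appendix 6 imposes mandatory actions which the NOTE breaches. The routing of liver tests to Appendix 6 does favour the specific rows for hepatic values. But a likely reading is not a stated order of precedence. A permission to continue and a direction to stop permanently cannot both guide the same decision, and the wrong appendix numbers weaken the argument that readers will reach the specific row.

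A reader might also infer that the NOTE permits full dosing throughout the Hy's Law pattern in Section 6.4.2.10. The documents do not support that. The combined AST/ALT and bilirubin row in Appendix 6 falls under the NOTE only where the event is Grade ≥3. Its thresholds also differ from those of Section 6.4.2.10, which uses at least 3 times baseline for the enzymes and at least 2 times ULN for bilirubin, with at least 35% of it direct.

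**Conclusion.** The inconsistency is real but narrow. Two laboratory-defined Grade ≥3 events are clear conflicts (AST/ALT above 10 times ULN; asymptomatic Grade 4 CPK), and one row conflicts in part. The NOTE also differs from two general rules: Table 3 and the Appendix 6 catch-all row. It merits correction because it bears on dosing safety and is cheap to resolve. The conclusion rests on reading study treatment in the NOTE as both drugs, and on there being no order of precedence in the text.

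Two larger claims should not be drawn from it.

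- **Effect on the safety stopping rule.** A reader might think that the toxicity rate monitored under Section 5.10.5 depends on which text is followed. It does not. That rule counts patients with a qualifying treatment-related event, and Grade ≥3 hepatotoxicity and elevated CPK are both listed. The patient enters the numerator when the event occurs, before any dosing decision, and is counted once.
- **Number of patients affected.** Section 2.7 reports Grade ≥3 CPK increase in 4.4% of 90 patients on the combination. Applied to 60 patients this gives 0.044 × 60 = 2.6. That is not the number in conflict: the figure includes Grade 3, and for asymptomatic Grade 3 CPK Appendix 6 agrees with the NOTE. The documents give no rate for asymptomatic Grade 4 CPK, AST/ALT above 10 times ULN or the combined pattern, so the number affected is unknown and could be zero.

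**What to change.** The sponsor and Medical Monitor should reconcile the third NOTE in Section 5.5.1 with Table 3 and with Appendix 6, and state in 5.5.1 which text governs hepatic and CPK laboratory values. The reconciliation must cover the Appendix 6 catch-all row as well as the event-specific rows; otherwise the conflict remains for every laboratory event without a row of its own. Whichever way the question is settled, the wording on the other side should be changed to match. The choice of rule is clinical and is left to them.

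The references to Appendix 7 for event management in Sections 5.5.2, 5.5.3, 5.5.4 and 6.1.2.5 should be corrected. Section 5.5.3 also cites Appendix 8 for anaphylaxis, which is now Biomarker Analysis, so the numbering looks shifted by one and should be checked throughout.

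The cost is a sentence or two in 5.5.1, any matching edit to Table 3 or Appendix 6, and the cross-reference corrections, all in one amendment. No procedures are added, and the sample size and analyses do not change.
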